Purpose of clinical trial	To investigate the cardio-metabolic health effects of consuming potatoes in place of other refined carbohydrate (pasta and rice), in healthy adults.
Primary objective	The primary objective of this proposal is to investigate whether consuming a portion of potatoes in the evening meal, in place of other refined carbohydrates, can improve sleep quality (measurable as the ratio of total sleep time in bed: "sleep efficiency"), and improve mean nocturnal glucose, both risk factors for cardiometabolic diseases.
Secondary objective (s)	To investigate the effects of regular white potato consumption on endothelium-dependent vasodilation (measured by flow-mediated dilatation) and other related biomarkers of cardio-metabolic disease risk, when compared to regular refined carbohydrate consumption.
Number of Participants	The study aims to recruit a total of 80 participants (allowing ~15% drop out rate), for an allocation of 1:1 intervention to control, to reach 80% power at a significance level of 0.025 (based on two outcomes).
Trial Design	A randomised, two-parallel arm, in clinic and remote, 12-week dietary intervention study.
Study arms	
1. Experimental: Habitual potato consumption.
 
At minimum of 230g white potatoes, including fresh and frozen, baked, boiled and mashed potatoes, will be consumed in the evening meal, in replacement of other starches.
 
2. Active Comparator: Habitual non-nutrient dense starch consumption.

	Isocaloric amount of non-nutrient dense starchy staples, such as white rice, white pasta, and white couscous, will be consumed during the evening meal.

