3.0 Study Objectives and Design

3.1 Study Objectives

To answer the following research questions:

Primary Objectives and endpoints (for detailed summaries of the outcomes, see section 3.3)

- 1) *Does regular consumption of white potatoes increase sleep quality, measurable as the ratio of total sleep time to time in bed: "sleep efficiency (SE)"?*
- 2) *Does regular consumption of white potatoes improve night-time glycaemic control compared with other, less nutrient dense starchy staples (white pasta, white rice etc.)?*

Secondary Objectives and endpoints

- 3) *Does regular consumption of white potatoes improve endothelial function?*
- 4) *Does regular consumption of white potatoes improve autonomic function?*
- 5) *Does regular consumption of white potatoes improve blood lipid profiles, and glucose control (fasting glucose, fasting insulin, glycated haemoglobin), when compared with other, less nutrient dense starchy staples?*
- 6) *Does regular consumption of white potatoes improve blood pressure?*

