Daytime glycaemic control: Additionally, we plan to look at the same markers across 12-day daytime and 24-hour period.

Endothelial function: Impaired nitric oxide (NO) production causes endothelial dysfunction and increases risk of CVD (55). Capacity to synthesize NO can be assessed by ultrasound imaging of brachial arterial diameter before and after hyperaemia to determine FMD, regarded as the most reliable *in vivo* index (56). Measurements (and blood samples) will be taken at the same approximate time of day to account for circadian fluctuations, and by the same operator to reduce measurement error. All videos will be analysed using a custom MATLAB program (VidArt V13.5, [name], Department of Biomedical Engineering, Maastricht University Medical Center (MUMC)+, Maastricht, The Netherlands)

Heart rate variability (HRV) and blood pressure (BP): Improved HRV, a parameter of cardiac autonomic function, and BP are plausible health benefits of white potato consumption due to increased potassium intakes. Previous intervention studies have reported an improvement in clinic BP following potato consumption (18); however, the effects of potato intake on HRV have not been investigated to our knowledge. HRV is an indirect measure of autonomic nervous system function and predictive of risk of sudden cardiac death (57).

HRV will be measured using a small wireless heart rate/ECG monitor that continuously records interbeat intervals (eMotion Faros 180, Mega Electronics Ltd) to calculate 48-h, daytime and night-time parameters using Cardiscope Analytics software (HASIBA Medical GmbH) (58) Building on prior HRV analysis expertise (58, 59, 60), this will provide novel data on a hitherto unexplored risk factor for hypertension, T2D, chronic kidney disease and CVD events in relation to potato consumption, and will provide important mechanistic information underpinning the 3 primary outcomes. BP will be measured at home using optical blood pressure monitoring via a bracelet. 2-hour averages will be obtained continuously for 12-weeks.

Diet quality will be measured using dietary indices associated with health including PDI (61) (uPDI, hPDI), aMED (62), aHEI (62) and HFD (63, 64) to demonstrate the impact of potatoes on overall diet quality and for inclusion as a covariate in analysis.

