4.0 Sample Size, Statistics, Selection and Withdrawal of Participants

4.1 Sample size

This study aims to recruit a total of 80 men and women, 1:1 intervention to control, to have 68 people (~15% dropout) complete the study. 34 people in each arm will provide 80% power to detect a difference of 0.468 mmol/L nocturnal glucose concentrations (SD 0.61), based on our CGM data from PREDICT 1 (unpublished data). Additionally, only 24 people are needed to provide 80% power to detect a difference of 4.2% sleep efficiency units, with SDs based on our previous sleep extension intervention (SLuMBER study) (7). These parameters are based on a significance level of 0.025, for two outcomes (calculated with *G*Power* software)

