4.2 Study statistical plan

Mean differences between groups will be assessed at endpoint, adjusting for baseline values and other potential other covariates (maximum 3, as per the rule of 1 covariate per 10 participants).

For the outcomes with 3 timepoints (urinary Na, K, Na:K and calystegines), this will be assessed using a using Linear mixed models (mixed command) with change being the dependent factor, participant ID as random effect, treatment and season as fixed effects, and baseline outcome as a covariate. Variables with 2 timepoints (all other outcomes) will be assessed with an ANCOVA regression model (regress command), with baseline as a covariate. BMI, sex and age may also be covariates depending on the balancing of the arms. Sex differences will also be explored in some outcomes with known sexual dimorphisms, with the use of a sex interaction term.

A 2 -sided P value <0.05 will be considered as showing statistical significance.

Normality will be assessed visually with histogram and Q-Q plot of residuals, and heteroscedasticity with a fitted-residual plot, to satisfy the model assumptions.

We will primarily analyse outcomes on an intention-to-treat basis, analysing participants as randomised. Per-protocol analyses—restricted to participants meeting prespecified adherence criteria—will be performed to assess robustness.

All statistics will be run on Stata/MP 18.0.

[figure not shown]

Figure 5. Flow chart of the recruitment procedures

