5.4 Randomisation Procedures

Participants will be randomised to either the intervention or control arm, with an allocation ratio of 1:1. A minimisation procedure will be used that considers gender, age, ethnicity, BMI) in the randomization, by using the Shiny App software, which can be accessed at:

https://fsella.shinyapps.io/VM_app/?_ga=2.186170153.125318758.1628174827-961835063.1626383516 (71).

Screening data will be entered into minimisation software, by the research lead (See randomisation SOP). This database will balance the treatment arms for the following variables:

1. *Gender*. 2 groups: Male; Female
2. *Age*. 2 groups: 40-59; 60-80 y
3. *BMI*. 2 groups: Healthy weight 18.5-24.9; Overweight-Obese ≥ 25

Randomisation codes will be generated by the software and recorded on the relevant documentation in the Case Report Form and enrolment log. The randomization protocol follows the same protocol as used previously by our group for a parallel, two-arm, randomized controlled trial (30) for which a study statistician was employed. It has not been deemed necessary to employ a study statistician on the current trial due to the similarity of the study design, but the protocol will be discussed with a statistician from the King's Joint Clinical Trials Unit.

Participants will be blinded to whether they are receiving the intervention or the control, but it is not possible to blind them to the food itself. Also, as the study team is limited by resources, observer blinding is also impossible; however, the researcher undertaking statistical analysis will be blinded prior to analysis using a second set of study ID codes. FMD analysis will be conducted through semi-automated software analyses, which will reduce bias.

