7.2 Serious Adverse Events

The Principal Investigators ([name] and [name]) will oversee the safety of the study, including careful assessment and appropriate reporting of adverse/serious adverse events (AEs, SAEs) (appendix 6), following the 'Adverse Events Form Guidance' and Adverse event flow diagram

(appendix 7), provided by KCL's Research Governance Office. Reports of SAEs will be submitted within 15 days of the principal investigator becoming aware of the event, using 'Serious Adverse Events Reporting Form'.

8. Ethics & Regulatory Approvals

The study will be conducted following the principles of the Declaration of Helsinki (2013), the principles of GCP and in accordance with all applicable regulatory requirements including but not limited to the UK policy framework for health and social care research and the Mental Capacity Act 2005.

This protocol and related documents will be submitted for review to Kings College London Health Faculties Research and Ethics subcommittee, Waterloo Campus, [name].

Any subsequent protocol amendments will be resubmitted for approval before implementation. The Principal Investigator will submit a final report at conclusion of the trial to the funder and the REC.

9. Data Handling

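### The trial is sized at 0.025 for each of two primary outcomes, but the only analysis rule is P<0.05, so the plan contradicts itself on when a primary result is positive

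*Combined protocol and SAP*

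**What the plan says.** **Sizing.** Section 4.1 gives 34 completers per arm for 80% power to detect a 0.468 mmol/L difference in nocturnal glucose (SD 0.61), and adds: "These parameters are based on a significance level of 0.025, for two outcomes". The synopsis row on number of participants agrees: "to reach 80% power at a significance level of 0.025 (based on two outcomes").

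**Analysis.** Section 4.2 has one sentence on significance: "A 2 -sided P value <0.05 will be considered as showing statistical significance". The synopsis row on statistical methodology repeats it and sends the reader to Section 4.2 for detail. Neither place names the outcomes to which the threshold applies.

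**Primary outcomes.** The synopsis and Section 3.3 list two: 7-day sleep efficiency and 12-day mean nocturnal glucose. The synopsis objective joins them in one sentence (sleep efficiency, "and improve mean nocturnal glucose, both risk factors for cardiometabolic diseases"). Section 3.1 puts them as two separate questions, the second being "Does regular consumption of white potatoes improve night-time glycaemic control compared with other, less nutrient dense starchy staples". Neither wording is a success rule, and there is none elsewhere. The heart rate variability paragraph of Section 3.3 speaks of information "underpinning the 3 primary outcomes", which does not match the two listed.

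**The concern.** A planning alpha does not bind the analyst; the decision rule in the analysis section does. Here the two differ. Given a primary P value of 0.04, an analyst following Section 4.2 would call it significant, while one holding to the level in Section 4.1 would not. Both could cite the protocol.

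Two things are at stake. First, if a positive result on either primary counts, following Section 4.2 as written roughly doubles the chance of a false positive primary finding compared with what the sample size assumes. Second, the threshold is still open late in the trial. Version 5.1 is dated 31 August 2025, after the estimated primary completion of 01/05/2025 in the synopsis. An unsettled threshold at that stage leaves room to settle it once the results are known.

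**Working it through.** **1. Reproduce the plan's own figure.**

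Inputs from Section 4.1: difference 0.468 mmol/L, SD 0.61, 80% power, 34 per arm, 68 completers, about 15% dropout. Sidedness is not stated there. The standardised difference is 0.468 / 0.61 = 0.767. Sample size per arm for a two-sample t-test (noncentral t):

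| Significance level | n per arm for 80% power | Power with 34 per arm |
|---|---|---|
| 0.025, two-sided | 34 | 80.5% |
| 0.025, one-sided | 28 | 87.6% |
| 0.05, two-sided | 28 | 87.6% |
| 0.05, one-sided | 22 | 93.1% |

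Only two-sided 0.025 gives 34. Recruitment also checks: 68 / (1 − 0.15) = 80. The 0.025 is therefore not a one-sided restatement of two-sided 0.05. It is 0.05 / 2, divided over two outcomes, as the synopsis says.

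**2. False positive rate when either primary counts.**

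For independent outcomes, with both null hypotheses true:
- at 0.05 each: 1 − (1 − 0.05)² = 9.75%
- at 0.025 each: 1 − (1 − 0.025)² = 4.94%

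The documents give no correlation between sleep efficiency and nocturnal glucose, so a range is assumed. For correlated outcomes the rate is 1 − P(|Z₁| < c and |Z₂| < c), with Z₁ and Z₂ bivariate normal and c the two-sided critical value.

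| Assumed correlation | 0.05 each | 0.025 each |
|---|---|---|
| 0 | 9.75% | 4.94% |
| 0.3 | 9.51% | 4.84% |
| 0.5 | 9.07% | 4.65% |
| 0.9 | 7.04% | 3.62% |

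Every value in the middle column exceeds 5%; every value in the right-hand column is below it. The 5% overall target is inferred from 2 × 0.025; the plan does not state it.

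**3. False positive rate if both primaries had to succeed.**

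With both nulls true, the chance that both are falsely positive at 0.05 each is 0.25%, 0.49%, 0.93% and 2.96% for the same four correlations. If only one null is true, it is at most 5%. There is no inflation under that rule, but then the split to 0.025 would have had no purpose.

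**4. What the disagreement looks like on the glucose scale.**

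With 34 per arm and SD 0.61, the standard error of an unadjusted difference is 0.61 × √(2/34) = 0.148, on 66 degrees of freedom.
- two-sided 0.05: 1.997 × 0.148 = 0.295 mmol/L
- two-sided 0.025: 2.294 × 0.148 = 0.339 mmol/L

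An observed difference between 0.295 and 0.339 mmol/L is positive under one rule and negative under the other. This is an illustration, because the planned analysis is ANCOVA. If 0.61 is the endpoint SD and the baseline–endpoint correlation is 0.5 (assumed), the residual SD is 0.61 × √(1 − 0.5²) = 0.528 and the band is about 0.256 to 0.294. Adjustment moves the band but does not remove it.

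**The case against.** The strongest reply is that this is an omission, not a contradiction. The sentence in Section 4.2 is generic and names no outcome, whereas the 0.025 is tied expressly to two outcomes. A sympathetic reader could take 0.05 as the general or overall level and 0.025 as its share for each primary, simply not carried forward into Section 4.2. That is probably what was intended. But no passage says so, and the synopsis sends readers to Section 4.2 for the analysis, where the only threshold is 0.05. Followed literally, the rule applies to the primaries too.

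Other points stand in part:
- The inflation depends on either primary being enough. If both must succeed, 0.05 each is valid. The plan is silent on this, and the 0.025 sizing points to the either-one reading.
- The two wordings of the objectives do not conflict. They show only that the success rule is missing.
- The glucose band rests on an unadjusted test, and Section 4.1 does not say whether 0.61 is an endpoint or a change SD. The band is illustrative, and the conclusion does not rely on it.
- The mention of three primary outcomes is probably leftover wording and is an editorial matter.
- Stating 0.025 for each primary does not by itself say whether one success is enough. It controls the error either way, but the success rule should still be written down.

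**Conclusion.** The concern holds: the analysis rule is wrong as written and must be fixed. If either primary can count as success, Section 4.2 allows a 9.75% to 7.0% chance of at least one false positive primary result over assumed correlations of 0 to 0.9, instead of 4.9% to 3.6%. These figures assume that both nulls are true and that an overall 5% level was intended. The conclusion of the trial changes only when a primary P value falls between 0.025 and 0.05, but in that range the document supports opposite answers.

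The sample size is sound for glucose and does not need to change. Nor does testing at 0.05 leave the trial underpowered: 34 per arm has 87.6% power at that level. The fault is confined to type I error and the decision rule.

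**What to change.** Replace the blanket sentence in both Section 4.2 and the synopsis with one rule along these lines: each of the two primary outcomes is tested two-sided at 0.025 and reported with a 97.5% confidence interval; P<0.05 applies to the secondary outcomes, which are not adjusted for multiplicity. Add a clause stating whether success on one primary is sufficient or both are required. A named procedure at overall 5%, such as Holm or Hochberg, would also serve if it is specified in advance. At the same time, correct the count of primary outcomes in Section 3.3.

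**Cost.** No extra participants, visits or data. The primary threshold becomes stricter than the current sentence, but at the level the sample size already assumes, and power for glucose stays at 80.5% with 34 per arm.

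**Timing.** Because the current version postdates the estimated primary completion, the change should be a dated amendment. Section 8 gives the route: "Any subsequent protocol amendments will be resubmitted for approval before implementation". The deadline follows from Section 5.4 (Randomisation Procedures), under which "the researcher undertaking statistical analysis will be blinded prior to analysis using a second set of study ID codes". The amendment should be on record before those codes are broken.

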4.6 Criteria for Premature Withdrawal

This is an 'Intention to treat study', participants will only be withdrawn for the reasons outlined below:

1. Participant voluntarily withdraws from the study.
2. Participant death.
3. Participant acquires any of the listed exclusion criteria.

4. Participant's well-being, in the opinion of the investigators, would be compromised by study continuation.

If participants wish to withdraw, details on their reasoning will be formally documented. If withdrawal occurs after screening but prior to baseline visits, data will not be used on this participant, however if they withdraw during the study, the data will only be receded upon request, as stipulated in the information sheet (appendix 1). Data will be unable to be receded when published, and this will be clearly outlined in the PIS, but all data will be fully anonymised as per GDPR protocol.

5. Study procedures

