3.2 Intervention overview

Table 1. Summary of the Starchy Study's arms and Interventions, as written on ClinicalTrials.Gov

Arms	Assigned Interventions
Experimental: Habitual potato consumption At least 230g of white potatoes, including fresh and frozen, baked, boiled, and mashed potatoes, will be consumed in the evening meal, in replacement of non-nutrient-dense starchy staples, for 12 weeks.	Dietary Supplement: Habitual potato consumption Potatoes are to be consumed in the evening meal, every evening for 12-weeks.
Active Comparator: Habitual non-nutrient-dense staple consumption Isocaloric amounts of non-nutrient-dense starchy staples, such as white rice, white pasta, and white couscous, will be consumed in the evening meal for 12 weeks.	Dietary Supplement: Habitual non-nutrient-dense staple consumption White rice, white pasta or white couscous are to be consumed in the evening meal, every evening for 12-weeks.

Dietary Intervention

The intervention (potato group) will consume 230 g white potatoes as one of their 5-a-day fruits and vegetables, providing ~1000 mg potassium (enough to increase national median intakes up to

recommended intakes) in their evening meal (25% of energy intake from carbohydrates, or 12.5% of total energy intake, including fresh and frozen baked, boiled, mashed potato products), whereas the control group will consume isoenergetic amounts of non-nutrient dense starchy staples (white pasta, white rice, or couscous).

Participants will be given £5 per week, in renumeration for the purchasing of the starchy component.

Although participants cannot be blinded to what they're consuming, they will be blinded to whether they are in the control or the intervention group, to reduce risks of bias.

We have chosen not to adjust for % estimated energy requirements as potatoes are typically eaten as a standard portion size (e.g., standard baked potato is ~200g), and this simplifies the intervention for the participant.

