3.8 Inclusion and exclusion criteria

- **Inclusion criteria**
 - Healthy adults
 - Aged 40-80 years old
 - Intake of ≤ 4 portions of fruits and vegetables (excluding potatoes) per day
 - Low sleep quality- $<85\%$ sleep efficiency score on the PSQI
 -
- **Exclusion criteria**
 - Shift workers and those with multiple jobs or carers who are required to wake through the night
 - Unwilling to refrain from dietary supplements
 - Unwilling to follow protocol and/or give informed consent
 - Diagnosed with Cardiovascular Disease (CVD), Type 2 Diabetes, Celiac disease, Insomnia, Sleep apnoea
 - Presence of gastrointestinal disorder
 - Users of drugs that are likely to alter gastrointestinal motility or nutrient absorption
 - History of substance abuse or alcoholism
 - Currently pregnant, planning pregnancy, breastfeeding or having had a baby 12-month prior
 - Weight change of $>3\text{kg}$ in preceding 2-months
 - $\text{BMI} <18.5\text{kg/m}^2$ or $> 35\text{kg/m}^2$,
 - Current smokers, or individuals who quit smoking in the last 6-months
 - Frequently consume wholemeal products (1-2 times per day, in the short screening FFQ)
 - Never consumed refined starchy staple, such as white pasta or rice (rarely or never, in the short screening FFQ)
 - High potato consumption (4-6 times per week, in the short screening FFQ)
 - High risk of obstructive sleep apnoea (answer yes to >3 questions, in STOP-Bang questionnaire)

V5.1 31/08/2025

NON-CTIMP randomised trial

Clinical Trials ref: NCT05994313

REC: HR/DP-22/23-35587

- Vegan
- Sleep-related medications, or medications that may interfere with sleep
- Fasting glucose >7mmol/l (finger prick test at baseline clinic)

Table 2. Event and Outcome matrix

Body composition (Tanita scales)	Researcher	Secondary outcome					✓						✓		
HRV (48-hours and acute response to stress)	Researcher	Secondary outcome					✓						✓		
Weight	Participant	Secondary outcome													✓
Blood pressure	(Automated via bracelet)	Secondary outcome												✓	
4-day food diary + appetite visual analogue scale	Participant Baseline and Endline: 24-hr before clinics Midline: taken at home and sample posted	Dietary data for quality indices/covariates PDI (uPDI, hPDI) aMED aHEI HFD					✓			✓			✓		

[figure not shown]

Figure 4. Flow diagram of RCT process.

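### Withdrawal reason 3 does not say which exclusion criteria apply after randomisation, so it can remove participants on outcome-related grounds and leave them without an endline value

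*Combined protocol and SAP*

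**What the plan says.** Section 4.6 calls the trial an intention-to-treat study and states that "participants will only be withdrawn for the reasons outlined below". Four grounds follow. The third is "Participant acquires any of the listed exclusion criteria", with no exceptions.

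The exclusion list in Section 3.8 mixes different kinds of item:

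- Some are tied to a screening instrument or the baseline visit. One is "High potato consumption (4-6 times per week, in the short screening FFQ"; others are the wholemeal and refined-starch items, the STOP-Bang score and the baseline finger-prick glucose.
- Others have no such label. They include a weight change of more than 3 kg over two months, diagnosed insomnia or type 2 diabetes, and "Sleep-related medications, or medications that may interfere with sleep".

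Section 3.2 assigns the diets. For one arm, "Potatoes are to be consumed in the evening meal, every evening for 12-weeks". For the other, "White rice, white pasta or white couscous are to be consumed in the evening meal, every evening for 12-weeks". The same section counts a participant as compliant at 75% or more of days, both overall and in the final four weeks.

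Section 4.2 makes intention-to-treat the primary analysis and uses ANCOVA, adjusted for baseline, for outcomes with two timepoints. The synopsis places both primary outcomes at baseline and endline only. Section 5.4 (Randomisation Procedures) says that observers cannot be blinded. Section 5.8 describes follow-up procedures as not relevant.

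**The concern.** A withdrawal rule that reaches every exclusion criterion is safe only if those criteria are unrelated to treatment and outcome, or if outcome data are still collected after withdrawal. Neither is assured here.

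A participant who starts a sleep-affecting medicine, or is diagnosed with insomnia, is likely to be among those sleeping worst. One diagnosed with type 2 diabetes is likely to be among those with the highest glucose. Weight change above 3 kg is movement in a listed secondary outcome. If such people leave before endline, the comparison of sleep efficiency and nocturnal glucose is made among those who did not deteriorate in these ways. If the diets affect how often this happens, the bias differs by arm.

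The documents do not say which criteria continue, so staff who know the allocation must decide case by case.

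**Working it through.** **1. The literal conflict with the potato diet.** Inputs: Sections 3.2 and 3.8.
- Assigned frequency: 7 evenings a week, or 7 × 12 = 84 evenings.
- Compliance threshold: 0.75 × 84 = 63 evenings; 63 / 12 = 5.25 a week.
- Listed exclusion: 4–6 times a week. Its lower bound corresponds to 4 / 7 = 57% adherence.

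Every potato-arm participant counted as compliant therefore averages above 4 a week. Controls reach no intake criterion through their assigned staple. However, the item is defined by an answer on the screening questionnaire. Sections 3.7 and 5.3 place that questionnaire before enrolment, and no section repeats it. Later diet is measured by recalls, diaries and a meal checklist. This item is plainly for entry only.

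**2. The unlabelled criteria.** Can they arise and be noticed on study?
- Weight change: the two-month window fits within the 12-week diet, and home weights are recorded throughout (Sections 5.4 and 5.6).
- Sleep-affecting medication: current medication is a case report form item (Section 9.2), and the urine form asks about medication at each of three collections (Appendix 5).
- Insomnia or type 2 diabetes: a diagnosis made outside the trial would count. Detection within the trial is limited. The bloods are sent for analysis in one batch (Section 6.1), and the endline visit lists no finger prick.

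**3. What withdrawal does to the analysis.** Section 4.6 keeps data already collected unless removal is requested. For a participant withdrawn before endline, that means a baseline value and no endline value. The ANCOVA in Section 4.2 needs both. That section gives no method for missing outcomes, and nothing says that endline measures continue after withdrawal.

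**4. The plan's own sample size.** Inputs (Section 4.1): difference 0.468 mmol/L, SD 0.61, alpha 0.025 (taken as two-sided), power 80%.
- n per arm = 2 × (2.241 + 0.842)² × (0.61 / 0.468)² = 32.3, so 33 by the normal approximation.
- With the noncentral t, power is 0.792 at 33 and 0.8055 at 34 per arm, which reproduces 34.
- 68 / (1 − 0.15) = 80, which reproduces the recruitment target.

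The sample size is not in question. It allows 40 − 34 = 6 losses per arm. Beyond that, if one arm lost a further 5 or 10 completers while the other kept 34, power would be 0.77 (29 v 34) or 0.72 (24 v 34).

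**5. Possible bias, illustrative.** If a share p of one arm is withdrawn and their mean endline glucose would have been D above that of those retained, the retained mean is too low by p × D. The documents give neither p nor D. Assume D = one SD = 0.61 mmol/L, withdrawals in one arm only, and no recovery through baseline adjustment:

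| Withdrawn of 40 | Shift (mmol/L) | Share of 0.468 |
|---|---|---|
| 1 | 0.025 × 0.61 = 0.015 | 3% |
| 3 | 0.075 × 0.61 = 0.046 | 10% |
| 6 | 0.150 × 0.61 = 0.092 | 20% |

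Equal withdrawal with an equal gap in both arms would cancel.

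**The case against.** The strongest defence is that no sensible team would misapply this rule. The trial has one centre and is run by the group that wrote the protocol, and Section 3.2 treats eating the assigned potatoes as compliance. This defence stands for the dietary items. A reader might infer from step 1 that reason 3 withdraws every adherent potato-arm participant and empties that arm. The documents do not support that: the item is a screening answer, and at full adherence the intake of 7 a week would fall in the questionnaire's daily column, not the 4–6 column.

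A reader might also infer that "Unwilling to follow protocol and/or give informed consent" turns non-adherence into withdrawal. Sections 3.2, 5.4 and 9.6 point the other way. Participants who struggle receive tailored advice and follow-up, and those below 75% are classified as non-compliant.

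A third tempting inference is that reason 3 is redundant because reason 4 covers medical grounds. Reason 4 is an investigator's judgement of well-being, which is not the same as a list of named conditions.

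It is also fair to say that few healthy, screened adults may acquire one of the unlabelled criteria in 12 weeks, and that the plan already expects about 15% dropout. The first part limits the size. The second does not answer the point, because this loss would be produced by the protocol's own rule, on grounds linked to outcome, and not by participants choosing to leave. Keeping earlier data and analysing as randomised do not supply a missing endline value.

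**Conclusion.** The concern holds as a minor to moderate defect. Reason 3 does not distinguish entry criteria from continuing ones. For the criteria with no screening label, it can cause withdrawals related to sleep, glycaemia or weight. An unblinded team decides them, and the participant is left without the endline value that the intention-to-treat analysis requires. The clash with the potato diet shows that the wording cannot be applied literally, but no loss of the potato arm is to be expected from it.

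The size cannot be fixed from the documents, which give no rate for any of these events. The 0.015 to 0.092 mmol/L range rests on the assumed one-SD gap and on withdrawals in one arm only. The conclusion also assumes that withdrawal ends outcome collection, which the documents neither state nor rule out.

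**What to change.** Reconcile Sections 4.6, 3.8, 3.2 and 4.2:

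- Mark each exclusion criterion in Section 3.8 as entry only or as applying during the study, and limit reason 3 to the second group. Which medical criteria stop the diet is for the investigators to decide. The PSQI threshold needs no mark, because it is an inclusion criterion and reason 3 does not reach it.
- State that stopping the diet does not end follow-up. Endline actigraphy and CGM are still collected where the participant agrees, and are analysed as randomised.
- If follow-up is already complete, which is possible since the synopsis estimates primary completion at 01/05/2025 and this version is dated 31 August 2025, report the withdrawals made under reason 3 by arm and by criterion.

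The cost is a short amendment and endline measures for what may be a few participants who have stopped the diet. It needs no extra recruitment and no visits beyond those already scheduled.
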